15.0 Recruitment Methods

15.1 Describe when, where, and how you will recruit potential subjects:

Recruitment will take place on a continuous basis. Recruitment efforts will include the following strategies: 1) Hard copy flyers. 2) Directly reaching potentially eligible university students through Ads in university-run Listservs 3) Ads in local newspapers. 4) Ads on social media, such as HNFE's and CHBR's Twitter and Facebook accounts. 5) Online story for recruitment avenues such as VT Daily News notices. Interested people will be directed to complete an online survey or contact the Project Director ([name], Clinical Studies Coordinator for HNFE) or Roanoke Study Coordinator, who will schedule an initial phone screening to determine eligibility.

15.2 Describe the source of subjects (for example, clinic patients with specific conditions, students in the library, community members at a gathering, or members of a local gym):

General population, Virginia Tech community, local community

15.3 Describe the methods that you will use to identify potential subjects:

Responses on the online or phone pre-screening form will be used to identify potential subjects.

15.4 Describe materials that you will be use to recruit subjects. Attach copies of these documents with this protocol in Protocol Management and be sure to include the IRB protocol number on each document.

- *For flyers, attach the final copy of printed flyers.*
- *For Virginia Tech News, Facebook postings and ads, newspaper ads, websites, MTurk/SONA/online survey systems, etc., attach the final wording and graphics to be used.*
- *For email recruitments, please include the subject line.*
- *For advertisements meant for audio broadcast, please submit the wording of the advertisement prior to taping (to avoid having to re-record with approved language) and submit the final recorded version for IRB review before use.*
- *Describe any compensation to subjects. Separate compensation into appropriate categories, such as: reimbursement for expenses, time and effort, and additional incentives for study participation. For each category, specify the amount (including any pro-rated amount), schedule, and method of payment.*

All recruitment advertisements and text for email recruitment are uploaded to Protocol Management.

Participants will receive a total of \$400 for completing the study as follows:

Upon completion of eligibility and screening visits, \$20.

Upon completion of diet period 1 , \$190.

Upon completion of Debrief and return of EAH take home box (end of feeding period 2), \$190.

Upon completion of two optional 24-hour urine collections, \$25 per collection.

Payments will be made using the ClinCard system.

Incentives for Completion:

A 3D printed brain will be used as an incentive for full completion of study and participants will be awarded their 3D printed version of their own brain as a completion bonus.

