11.0 Study Timelines

11.1 *Describe:*

- *The duration of an individual subject's participation in the study (for example, 1 hour, 2-4 weeks, 3-5 years).*

- *The amount of time expected to enroll all study subjects (weeks, months, years, etc.)*
- *The amount of time expected for the investigators to complete this study including primary data analyses.*

The total estimated duration for individual participants is ~10-12 weeks involving 1-2 weeks of screening and baseline testing followed by 2, 14-day feeding periods; followed by 2 days of post-intervention testing and a 4 week washout period in between feeding conditions. The number of study visits will be ~34 and the total number of hours required for participation will be ~33-35 hours.

Approximately 1 year will be required to recruit and enroll participants. Approximately 1.5 - 2 years will be required to complete the study data collection and analysis. If recruitment goals are not met within 2 years, a 1-year no-cost extension will be requested from the NIH if study funds are available to continue recruitment and complete data collection/analysis.

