Safety of Proposed Research Diet: We are providing participants with an amount of food required to maintain their body weight. As such, there should be no weight gain. Research dietitians and dietetic technicians will be monitoring the body weight of all subjects on a daily basis. In the event that energy requirements are overestimated, participants will be instructed to return un-eaten food to our metabolic kitchen. In the event of weight loss or reports of substantial hunger, diets will be adjusted to provide additional calories. Safety will be further ensured by: a) only recruiting individuals without extreme dietary patterns; b) minimizing the duration of the intervention period as much as possible while also ensuring sufficient time to observe changes in our primary outcome measures; and c) only recruiting healthy individuals. While there is a risk of food poisoning, food allergies, and gastrointestinal discomfort with research diet administration, these will be minimized by: a) having all diets prepared and packaged in our metabolic kitchen by ServSafe-certified staff. The Metabolic Kitchen is located on the Virginia Tech campus, directed by [name], RD who has over 20 years of experience conducting clinical research, designing and preparing research diets; b) designing diets based on participant's food preferences to the extent possible; and c) conducting a detailed interview with all subjects before starting the study to screen for known food allergies, sensitivities, or aversions. List of foods to be used on the controlled diets will be reviewed with participants prior to enrollment. Risk of food-borne illness will be minimized by training research staff on proper food handling, preparation, and storage etc. protocols consistent with ServSafe food safety guidelines. To minimize risk of participants engaging in improper food safety practices, food will be provided in temperature-controlled coolers and information regarding proper storage and reheating of foods will be provided.

The intervention and measurement protocols pose minimal risk to participants. The data safety monitoring plan (DSMP) for this study focuses on close monitoring by the MPI and the safety officer, along with prompt reporting of excessive adverse events and any serious adverse events (AEs) to the NIH and to the Institutional Review Board at Virginia

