sign an informed consent document detailing the previously mentioned information. A copy of the consent document will be provided for participants to take with them.

Non-English Speaking Subjects

- *Indicate what language(s) other than English are understood by prospective subjects or representatives.*
- *If non-English speakers will be recruited, describe the process you will use to ensure that the oral and/or written consent information provided will be in a language that they understand.*
- *If you translate consent forms and study materials, please provide a certified translation of the form as well as the certification document.*
- *Indicate the spoken language that study personnel obtaining consent will use. Describe how you will assess fluency of personnel obtaining consent to ensure that the translation is accurate.*

N/A

Waiver or Alteration of Consent Process (consent will not be obtained, required information will not be disclosed, or the research involves deception)

- *Review the “CHECKLIST: Waiver or Alteration of Consent Process (HRP-410)” to ensure you have provided sufficient information for the IRB to make these determinations (i.e., that it meets the criteria for a waiver or alteration of the consent process).*

The study name on recruitment and consent form materials will be Young Adults Eating Habits (YAEH) so as to keep participants somewhat naive about the exact focus of our study, which is the impact of ultra-processed food exposure on energy (kcal) intake and food selection. There will be an alteration of the consent process for this study.

Participants will receive incomplete information about the purpose behind the ad libitum food intake measure at the buffet meal and the eating in the absence of hunger measure collected following the buffet meal. Participants will not be informed that their food consumption will be measured during both of these portions of the study; this will be done covertly by research staff when the participant leaves the room. This alteration is necessary because the ad libitum food intake aim could not be practically carried out without withholding this information. Knowing the purpose of the study could impact participants' food selection and intake at the buffet meal, which will impact study results.

Following their participation in the study, participants will be given additional information about the measures associated with the buffet meal and snacks. This

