debriefing process will include providing them with a debriefing document, and they will be given the opportunity to withdraw these data from the study. They will be asked to sign this document to indicate that they agreed to have their data used. Either the MPI or the study coordinator will provide disclosure on the true purpose of this study visit.

Subjects who are not yet adults (minors: infants, children, teenagers)

- *Describe the criteria that you will use to determine legal age for consent to treatments or procedures involved in the research under the applicable law of the jurisdiction in which the research will be conducted (e.g., in Virginia, individuals under the age of 18 years).*
 - *For research conducted in Virginia, review “SOP: Legally Authorized Representatives, Minors, and Guardians (HRP-013)” to determine which individuals in the state meet the definition of “minor.”*
 - *For research conducted outside of the state, please describe the legal requirements for the definition of “minor.”*
- *Describe the process for obtaining parental permission.*
 - *Permission from one parent is acceptable for studies that involve no greater than minimal risk OR involve greater than minimal risk but present the prospect of direct benefit to the minor subject.*
 - *Permission from both parents is required in all other cases (unless one parent is deceased, unknown, incompetent, or not reasonably available, or when only one parent has legal responsibility for the care and custody of the minor).*
- *Describe whether you will obtain permission from individuals other than parents or Legally Authorized Representatives, and if so, who will be allowed to provide permission. Describe the process you will use to determine these individuals’ authority to consent to the minor’s general medical care.*
- *Indicate whether you will obtain assent from all, some, or none of the minors. If you will obtain assent from some minors, indicate which minors will be required to assent. Consider chronological age and intellectual capacity when determining who will be required to provide assent (e.g., infants are unable to assent. However, teenagers are likely able to read and sign an assent form).*
- *When assent of minors is obtained, describe whether and how you will document it. Will minors sign an assent form or give verbal assent?*
- *Attach parental permission and minor assent forms or scripts in Protocol Management.*

N/A

Adults Unable to Consent

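### Completers are told about the covert intake measurement while recruitment is still open, and the protocol describes no confidentiality request, awareness check or analysis by awareness

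*Combined protocol and SAP*

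**What the plan says.** Sections 8.6 and 24.1 justify altering consent on the ground that the intake aim depends on participants not knowing that their eating is measured. Section 24.1 says such knowledge could affect "food selection and intake at the buffet meal, which will impact study results". Three protections are described: a neutral study name, not presenting the meal as an ad libitum buffet, and covert weighing.

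Disclosure is individual. The last payment in Section 15.4 falls due "Upon completion of Debrief and return of EAH take home box (end of feeding period 2", and the Section 8.2 schedule puts the debrief in the second diet period. Section 24.1 adds: "Either the MPI or the study coordinator will provide disclosure on the true purpose of this study visit". As described in Sections 8.6 and 24.1, the debrief explains what was withheld, offers withdrawal of those data and takes a signature.

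Recruitment is rolling (Section 15.1: "Recruitment will take place on a continuous basis"). One channel is "Directly reaching potentially eligible university students through Ads in university-run Listservs", and Section 15.2 gives the source as "General population, Virginia Tech community, local community". On duration, Section 11.1 says "Approximately 1 year will be required to recruit and enroll participants", and Section 26.1 calls 1 to 1.5 years feasible.

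The analysis plan in Section 5.2 does not mention awareness.

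**The concern.** All three protections act before a participant's own debrief. None limits what a debriefed participant may say to someone who has yet to eat at a buffet. Contact is plausible: participants on a diet eat breakfast in one dining laboratory Monday to Saturday (Section 8.2), and many will come from one campus.

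Someone who knows that intake is recorded may eat differently at both buffets, which would tend to shrink the within-person diet difference. Someone who learns between the two buffets would add a period shift. Awareness can also arise without leakage, because after the first buffet each participant hands a snack box back to staff.

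Without awareness data, a null or small Aim 2 result could not be told apart from failed masking, and the report could not show that measurement was covert in practice. What a participant believed before the disclosure cannot be recovered afterwards.

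**Working it through.** The plan gives no figure for leakage, so there is nothing to reproduce. Two checks are possible.

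**1. How much of the trial follows the first debrief?**

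Inputs:
- 32 participants (Section 14.1).
- Enrolment over T = 52 to 78 weeks (Sections 11.1 and 26.1).
- Participation of D = 10 to 12 weeks, with the debrief at the end (Sections 11.1 and 15.4).
- First buffet s = 3 to 4 weeks after entry: 1-2 weeks of screening plus the 14-day diet.
- Assumption: evenly spaced entry, t_i = i × T/31 for i = 0 to 31, so one entry every 1.68 weeks (T = 52) or 2.52 weeks (T = 78).

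The first debrief is at week D. A first buffet follows it when t_i + s > D.

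| T (weeks) | D (weeks) | Entries after first debrief | First buffets after it (s = 3; s = 4) |
|---|---|---|---|
| 52 | 10 | 26 | 27; 28 |
| 52 | 12 | 24 | 26; 27 |
| 78 | 10 | 28 | 29; 29 |
| 78 | 12 | 27 | 28; 28 |

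So 26-29 of 32 first buffets (81-91%) follow the first debrief.

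For second buffets, equal durations put everyone after the first participant later than the first debrief: 31 of 32. The lowest count arises if the first participant takes 12 weeks, the others take 10 and T = 52. The second entrant then finishes at 1.68 + 10 = 11.68 weeks, before week 12, which leaves 30 of 32.

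Some overlap does not depend on even spacing. The kitchen can feed 10-12 people per day (Section 26.1), so 32 cannot be fed at once.

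**2. What would leakage do to Aim 2?**

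Section 14.1 gives 13 participants for the secondary aim and 26 completers, but no alpha, power or effect size for Aim 2. Assume a two-sided 5% paired t-test and 80% design power. Power is the upper tail of a noncentral t with n − 1 degrees of freedom and noncentrality d√n, beyond t(0.975, n − 1).

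- n = 13: critical value 2.179; 80% power requires d = 0.847.
- n = 26: critical value 2.060; noncentrality 0.847 × √26 = 4.317; power 98.6%.

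Let q be the share aware, and suppose their diet contrast is exactly zero. The mean difference becomes (1 − q) times its value. The standard deviation is held fixed for simplicity.

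| q | d(1 − q) | Noncentrality | Power, n = 26 |
|---|---|---|---|
| 0 | 0.847 | 4.317 | 98.6% |
| 10% | 0.762 | 3.885 | 96% |
| 20% | 0.677 | 3.454 | 91% |
| 30% | 0.593 | 3.022 | 83% |

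The estimate shrinks by 10%, 20% or 30%, while power stays above 80%.

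**The case against.** **Protections exist.** A reader might infer that masking is unprotected. The documents do not support that: the three measures above are real, and Section 24.1 aims only to keep participants somewhat naive. The gap is limited to disclosure by completers and to checking awareness.

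**The debriefing document and the Manual of Procedures were not supplied.** A confidentiality request may already be in one of them. This stands, so the point is about what the protocol describes.

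**Leakage is not shown to occur.** The counts are of buffets held after a single person has been told. A reader might take them as the share of compromised meals, which they are not. Recruitment also uses local newspapers and reaches the general population, so participants need not know each other. This stands.

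**Aim 2 has power to spare.** A reader might infer a serious loss of power, for example by taking the effect detectable with 26 people. That number was set for the primary imaging aim; the Aim 2 figure is 13, and on that basis no power problem appears up to 30% aware. The zero-contrast model is also extreme. If awareness only attenuates, a positive result is conservative. All of this stands, but it does not remove the bias or make a null result interpretable.

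**Other passages may look related.** Section 13.1 is answered N/A, but its prompt concerns undue influence, not masking. Section 17.2 says "List of foods to be used on the controlled diets will be reviewed with participants prior to enrollment", but nothing there says that the list shows the diet contrast or the intake measurement. Neither supports this point.

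**Conclusion.** The point holds in a limited form. The protocol makes Aim 2 depend on participants not knowing about the measurement, discloses it person by person while recruitment is open, and describes no confidentiality request, awareness check or analysis by awareness.

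The opportunity is large under even enrolment, but actual exposure is unknown. The consequence is possible bias towards zero, equal to the share aware under the extreme model, and masking that cannot be verified. It concerns secondary and exploratory intake outcomes: the buffet and eating in the absence of hunger. Nothing here bears on the primary fMRI endpoint or shows a loss of planned power. It is an optional, low-cost improvement.

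**What to change.** 1. Unless the debriefing document already contains it, add a request not to discuss the intake measurement with others until enrolment closes.
2. At the same visit, before disclosure, ask one open question: what the participant thought the buffet and snack sessions were for, whether anyone had told them, and if so whether before the first or the second buffet. Have the answers coded without knowledge of diet sequence.
3. Report the proportion aware, and prespecify a sensitivity analysis of buffet and snack outcomes that excludes aware participants.

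The debrief and the right to withdraw data stay as they are, and no visit or participant is added. The cost is one sentence, one question, its coding and slightly more analysis.

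There are two limits. Recall of when awareness arose will be imperfect, so a shift between buffets may not be fully resolved. The sensitivity analysis will also be smaller: from 26 completers, about 23, 21 or 18 remain at 10%, 20% or 30% aware (26 × 0.9 = 23.4; 26 × 0.8 = 20.8; 26 × 0.7 = 18.2). It should support the main analysis, not replace it.

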16.0 Withdrawal of Subjects

16.1 Describe circumstances under which you anticipate subjects could be withdrawn from the research without their consent:

Non-compliance with study procedures, including consumption of the controlled diets. As is standard with MRI research, if subjects experience unusual sensations, they will be withdrawn. In some cases, due to the magnetic field (as described in risks below) subjects may experience peripheral nerve stimulation, e.g. tingling or twitching. They will be withdrawn from the study if this occurs.

16.2 If applicable, describe any procedures for orderly termination (e.g., discontinuation of a study drug or debriefing after a behavioral intervention):

Participants will be provided with an informational packet containing a summary of their body weight and composition and usual dietary intake. The packet will contain reference values, if available, and current recommendations from major health or federal organizations such as the Dietary Guidelines for Americans 2020-2025.

16.3 Describe procedures that you will follow when subjects withdraw from the research, including partial withdrawal from procedures with continued data collection (e.g., participant declines to continue with regular blood draws, but continues with periodic behavioral questionnaires):

The following steps will be taken in the event a participant withdraws from the study and informs us they want their information destroyed:

1. The participant database will be updated that the participant withdrew (for all withdrawals).
2. Participant will be compensated for their time and sessions completed up to time of withdrawal. There will be no partial withdrawal.

17.0 Risks to Subjects

17.1 List the reasonably foreseeable risks, discomforts, hazards, or inconveniences to the subjects related to the subjects' participation in the research. Include for the IRB's consideration a description of the probability, magnitude, duration, and reversibility of the risks. Consider physical, psychological, social, legal, privacy, and economic risks. Do not indicate "No risk" or "N/A." Instead, for studies with very low risk (e.g., anonymous online questionnaire on a mundane topic) indicate "The investigators are not aware of any risks from participation in this study." or "No more than risks than are found in everyday life." The example

consent form presents a tabular method for risk information, which you can also use here. Common risk types include:

- *Physical (e.g., potential for pain, discomfort, infection)*
- *Psychological (e.g., potential for stress, discomfort, and/or embarrassment)*
- *Social (e.g., potential for discrimination or stigmatization and disruption of personal and family relationships)*
- *Legal (e.g., potential for disclosure of illegal activity, negligence)*
- *Privacy (e.g., potential for personal information being accessed, used, or disclosed without the subjects' knowledge or consent, breach of confidentiality/security)*
- *Economic (e.g., potential for individuals to lose access to economic services, employment, insurability)*

Food Consumption: There is risk of an allergic reaction to study provided meals if a participant has an unknown food allergy. There is also a risk of food-borne illness due to improper food preparation, storage, and handling on the part of both research staff and participants.

MRI data collection: The risks associated with fMRI are the same as those with conventional MRI. Movement or heating of metallic implants is a potential risk, therefore subjects will be screened to exclude people with metallic implants, fragments, or pacemakers. Some individuals may experience claustrophobic reactions in the scanner. Any subject experiencing claustrophobia will be removed from the scanner immediately.

The fMRI scanner produces loud noises which could be harmful to the subject. Participants will be required to wear headphones and earplugs to minimize the noise generated by the scanner.

The Siemens 3 T scanner has been approved by the FDA. However, there may be additional risks associated with scanning at 3.0 T compared to the conventional clinical scanners in the 1.5-2.0 T range. These include:

1. Effect of the static field. There is no conclusive evidence for irreversible or hazardous bioeffects to acute, short-term exposures of humans up to 2.0 T (Shellock and Kanal, 1996). Studies have indicated some side-effects at 4.0 T, namely unusual sensations including nausea, vertigo, and metallic taste (Schenck, 1991). However, there is no evidence that this is either irreversible or harmful. If subjects experience unusual sensations, they will be withdrawn.

2. Effect of the gradient field. MRI operates by rapidly changing small additional fields, called gradients. This will induce small electrical currents in any conductor, and thus could theoretically induce mild peripheral nerve stimulation. However, this is not substantially different at higher magnetic fields since the gradients are separate from the main magnet. There is no evidence that the effect of the gradients is any different at 3 T

than at 1.5 T. However, if subjects experience peripheral nerve stimulation, e.g. tingling or twitching, they will be withdrawn.

3. Effect of the RF electromagnetic field. The higher magnetic field strength requires that higher RF frequency pulses are used to excite the protons in the subject's brain. The limits of RF energy that can be safely given to humans has been clearly defined by the FDA: a). The exposure to RF energy below the level of concern is an SAR of 0.4 W/kg or less averaged over the body, and 8.0 W/kg or less spatial peak in any 1 g of tissue, and 3.2 W/kg or less average over the head; or b). The exposure to RF energy that is sufficient to produce a core temperature increase of 1 degree C and localized heating to no greater extent than 38 degrees C in the head, 39 degrees C in the trunk, and 40 degrees C in the extremities, except for patients with impaired systemic blood flow and/or perspiration. We will adhere to the recommendations for the head, which is also monitored by a Siemens built-in monitor.

4. Acoustic Noise Levels. Rapid changes in the currents in the gradient coils of the MRI scanner produce significant levels of acoustic noise. The levels of noise range approximately between 65 and 95 dB, but could have higher peaks. Communications with subjects takes place with the standard pneumatic headphones provided by the scanner manufacturer. These headphones provide some degree of noise reduction. Foam ear plugs with a Noise Reduction Rating of 31 dB will be provided.

Subjects may experience discomfort, such as anxiety during the MRI scanning. Subject comfort will be reassessed and subjects will be allowed to discontinue any session at any time.

The subject may communicate with the experimenter at any time: 1) before, in between, or after a scan via an intercom device between the scanner and control room, and 2) during a scan via a pneumatic squeeze bulb located in the scanner that triggers an alarm in the control room. Subjects who report discomfort and wish to discontinue their participation will be immediately withdrawn from the scanner. Subjects who are withdrawn from the study will be compensated for their participation to that point.

Milkshake stimuli: All components of the beverage stimuli are readily available outside the laboratory (grocery stores, etc.) and are likely already consumed by the participants. There are no known risks associated with these stimuli.

17.2 Indicate the measures you will use to minimize risks and monitor subjects for safety. (e.g., asking a subject at regular intervals to rate how they are feeling from 1 to 10, or to slowly crouch in order to check their balance.)

MRI: In order to minimize noise from the MRI scanner that can be potentially harmful for the subject, all subjects will be required to wear ear protection while in the scanner. The subject may communicate with the experimenter at any time: 1) before, in between, or after a scan via an intercom device between the scanner and control room, and 2)

during a scan via a pneumatic squeeze bulb located in the scanner that triggers an alarm in the control room. Subjects who report discomfort and wish to discontinue their participation will be immediately withdrawn from the scanner. Subjects who are withdrawn from the study will be compensated for their participation to that point.

Advanced MR/Operator Training: Required for those persons wishing to conduct research on the HNL MRIs. Training will consist of presentations, observation, and hands-on practice. Topics will include safety and emergency procedures, subject screening and preparation, scanner set-up and operation, and troubleshooting. Each person must also complete at least 4 hours of observation (to include 2 different studies) and at least 16 hours of supervised scanning (to include 4 different studies). Certification will be granted upon completion of the training and passing of a competency exam.

Informed Consent Process: Prior to participation in the study, participants will review and sign an informed consent document detailing the previously mentioned information on risks. A copy of the consent document will be provided for participants to take with them.

Safety of Proposed Research Diet: We are providing participants with an amount of food required to maintain their body weight. As such, there should be no weight gain. Research dietitians and dietetic technicians will be monitoring the body weight of all subjects on a daily basis. In the event that energy requirements are overestimated, participants will be instructed to return un-eaten food to our metabolic kitchen. In the event of weight loss or reports of substantial hunger, diets will be adjusted to provide additional calories. Safety will be further ensured by: a) only recruiting individuals without extreme dietary patterns; b) minimizing the duration of the intervention period as much as possible while also ensuring sufficient time to observe changes in our primary outcome measures; and c) only recruiting healthy individuals. While there is a risk of food poisoning, food allergies, and gastrointestinal discomfort with research diet administration, these will be minimized by: a) having all diets prepared and packaged in our metabolic kitchen by ServSafe-certified staff. The Metabolic Kitchen is located on the Virginia Tech campus, directed by [name], RD who has over 20 years of experience conducting clinical research, designing and preparing research diets; b) designing diets based on participant's food preferences to the extent possible; and c) conducting a detailed interview with all subjects before starting the study to screen for known food allergies, sensitivities, or aversions. List of foods to be used on the controlled diets will be reviewed with participants prior to enrollment. Risk of food-borne illness will be minimized by training research staff on proper food handling, preparation, and storage etc. protocols consistent with ServSafe food safety guidelines. To minimize risk of participants engaging in improper food safety practices, food will be provided in temperature-controlled coolers and information regarding proper storage and reheating of foods will be provided.

The intervention and measurement protocols pose minimal risk to participants. The data safety monitoring plan (DSMP) for this study focuses on close monitoring by the MPI and the safety officer, along with prompt reporting of excessive adverse events and any serious adverse events (AEs) to the NIH and to the Institutional Review Board at Virginia

Tech (VT IRB). All serious AEs will be reported by the PI within 48 hours of occurrence to the VT IRB. Safety reports will be sent to the MPI and MD safety officer. The MPI will be responsible for assembling the data and producing these reports as well as assuring that all parties obtain copies of these reports. Reports will be submitted annually to the VT IRB for review. The frequency of data review for this study differs according to the type of data, the availability of data collected, and the perceived level of risk. Participants will be queried at each laboratory visit when meals are picked up as to any side effects or changes in health status that they experience, over the two 2-week controlled feeding interventions.

Any reported side effects will be discussed immediately with the MPI and the safety officer. The safety officer will determine if medical intervention or other actions are warranted. Participants will be referred to their primary care physicians if there are incidental findings.

Data type	Frequency of reviewing reports
Subject accrual (adherence to the protocol regarding demographics, inclusion/exclusion)	Semi-annually
Adverse event rates	Semi-annually
Compliance to treatment	Semi-annually
Out of range laboratory data	Semi-annually
Stopping rules report regarding statistical power implications of drop outs and missing data	Semi-annually
Side effects of controlled diet, study procedures	Daily, when meals are picked up

17.3 If applicable, indicate which procedures might have risks to the subjects that are currently unforeseeable. This will be rare, and usually applicable when testing a new drug or device or a new use of an existing drug or device:

N/A

17.4 If applicable, indicate which procedures might have risks to an embryo or fetus should the subject be or become pregnant:

17.5 If applicable, describe risks to others who are not subjects (e.g., collection of sensitive health data that might affect sexual partners if disclosed, mandatory reporting of abuse, DNA testing that might affect family members or relationships):

N/A

